7.2 EXCLUSION CRITERIA

Patients who have met all the above inclusion criteria listed in [Section 7.1](#) will be screened for the following exclusion criteria which are sorted and numbered in the following subsections:

7.2.1 Exclusion criteria related to study methodology

- E 01. Organ transplantation recipient (except corneas, unless it is within 3 months prior to baseline visit).
- E 02. Major ischemic event, unrelated to GCA, within 12 weeks of screening.
- E 03. Any prior use of the following therapies, for the treatment of GCA:
- Janus kinase (JAK) inhibitor (eg, tofacitinib) within 4 weeks of baseline.
 - Cell-depletion agents (eg, anti CD20) without evidence of recovery of B cells to baseline level.
 - Abatacept within 8 weeks of baseline.
 - Anakinra within 1 week of baseline.
 - Tumor necrosis factor (TNF) inhibitors within 2 to 8 weeks (etanercept within 2 weeks; infliximab, certolizumab, golimumab, or adalimumab within 8 weeks), or less than at least 5 half-lives have elapsed prior to baseline, whichever is longer.
- E 04. Therapeutic failure, including inadequate response or intolerance, or contraindication, to biological IL-6/(R) antagonist (prior experience with IL-6/(R) antagonist that was terminated for reasons unrelated to therapeutic failure at least 3 months before baseline is not exclusionary).

- E 05. Use of any alkylating agents including cyclophosphamide (CYC) within 6 months of baseline.
- E 06. Use of immunosuppressants, such as hydroxychloroquine (HCQ), cyclosporine (CsA), azathioprine (AZA) or mycophenolate mofetil (MMF) or leflunomide (LEF) within 4 weeks of baseline.(Use of MTX not exceeding 25 mg per week and have been stable for at least 3 months prior to baseline is not exclusionary [see [Section 8.8](#)]).
- E 07. Concurrent use of systemic CS for conditions other than GCA.
- E 08. Use of IV CS at a dose equivalent to 100 mg of methylprednisolone or higher within 8 weeks of baseline for GCA therapy.
- E 09. Participation in any clinical research study that evaluated an investigational drug or therapy within 5 half-lives or 60 days of the screening visit, whichever is longer.
- E 10. History of alcohol or drug abuse within 5 years prior to the screening visit.
- E 11. Patient who withdraws consent during the screening period (following signing of the informed consent form).
- E 12. Based on Investigator judgment, conditions/situations such as:
 - Patients with short life expectancy
 - Patient is the INVESTIGATOR or any subinvestigator, Research Assistant, Pharmacist, Study Coordinator, other staff or relative thereof, directly involved in the conduct of the study, or, as applicable to employee of site/Investigator or Sponsor.
 - Uncooperative, or any condition, that could make the patient potentially noncompliant to the study procedures, etc, and individuals who are institutionalized due to regulatory or legal order.

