---------------------	---

STUDY POPULATION
 
Main selection criteria
	
Inclusion criteria:
 
• Diagnosis of GCA classified according to the following criteria:
- Age \geq50 years- History of ESR \geq50 mm/hour (or CRP $>$25 mg/L)- Presence of at least one of the following: Unequivocal cranial symptoms of GCA (new onset localized headache, scalp or temporal artery tenderness, ischemia-related vision loss, or otherwise unexplained mouth or jaw pain upon mastication) or symptoms of polymyalgia (defined as shoulder and/or hip girdle pain associated with inflammatory stiffness).- Presence of at least one of the following: Temporal artery biopsy revealing features of GCA; Evidence of large-vessel vasculitis by angiography or cross-sectional imaging (angiography, computed tomography angiography [CTA], magnetic resonance angiography [MRA], or positron emission tomography-computed tomography [PET-CT], ultrasound).• New onset active disease or refractory active disease according to the following criteria:
- New onset active disease is defined as: Diagnosis within 6 weeks of baseline.- Refractory active disease is defined as: Diagnosis $>$6 weeks before baseline and previous treatment with \geq40 mg/day prednisone (or equivalent) for at least 2 consecutive weeks at a time. This includes patients who have achieved remission in the past but have a flare in the disease again or patients who have not been able to achieve complete remission since diagnosis of GCA.• At least one of the following symptoms of GCA within 6 weeks of baseline:
- Unequivocal cranial symptoms of GCA (such as new onset localized headache, scalp or temporal artery tenderness, ischemia-related vision loss, or otherwise unexplained mouth or jaw pain upon mastication).- Unequivocal symptoms of polymyalgia rheumatica (PMR) (defined as shoulder and/or hip girdle pain associated with inflammatory stiffness).- Other features judged by the Investigator to be consistent with GCA or PMR flares (ie, new or worsened extremity claudication, fever not associated with infection).• Either ESR \geq30 mm/hour or CRP \geq10 mg/L within 6 weeks of baseline.• Receiving or able to receive prednisone 20 to 60 mg/day for the treatment of active GCA. 
Note: Sites that will consider inclusion of patients in the study using ultrasound as part of screening and diagnostic process for relevant disease status confirmation should only employ this method following completion of certification by the Sponsor (details of the ultrasound certification process are found in the manual).

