--	---

	
Exclusion criteria:
 
 • Organ transplantation recipient (except corneas, unless it is within 3 months prior to baseline visit). • Major ischemic event, unrelated to GCA, within 12 weeks of screening. • Prior treatment with any of the following: 
 - Janus kinase (JAK) inhibitor within 4 weeks of baseline. - Alkylating agents including cyclophosphamide within 6 months of baseline. - Tumor necrosis factor (TNF) inhibitors within 2 to 8 weeks of, or less than at least 5 half-lives have elapsed prior to, baseline, whichever is longer. - Abatacept within 8 weeks of baseline. - Anakinra within 1-week of baseline. • Therapeutic failure with biological Interleukin 6/(R) (IL-6/(R) antagonist. • Evidence of serious, uncontrolled concomitant disease (eg, cardiovascular, respiratory, hepatic, renal, endocrine, etc.).

Total expected number of patients
	
Approximately 360

STUDY TREATMENT(s)
 
Investigational medicinal product-1
 
Formulation:
 
Route(s) of administration:
 
Dose regimen:
 
Investigational medicinal product-2:
 
Formulation:
 
Route(s) of administration:
 
Dose regimen
 
Noninvestigational medicinal product(s):
	
Sarilumab or placebo.
 
Single-use prefilled glass syringes of sarilumab 200 mg, sarilumab 150 mg or matching placebo for sarilumab.
 
Subcutaneous (SC) route, in abdomen or thigh, or upper arm.
 
Sarilumab 200 mg, sarilumab 150 mg or matching placebo is to be administered q2w.
 
Prednisone or placebo
 
Over-encapsulated tablets/tablets/capsule
 
Oral
 
During the open-label prednisone period:
 
 • Prednisone once a day with dose level from 20 to 60 mg depending on the starting prednisone dose at randomization 
During the double-blind prednisone period:
 
 • Prednisone and/or matching placebo, once a day with dose level as per the prednisone protocol defined tapering regimen. 
The chosen rescue therapy, including CS, as per Investigator judgment.

ENDPOINT(S)
	
Primary endpoint:
 
Proportion of patients achieving sustained remission at Week 52. Sustained remission at Week 52 is defined by having met all of the following parameters:
 
 • Achievement of disease remission no later than Week 12. 
AND

[figure not shown]

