- E 17. Patients with fever associated with infection ($>38^{\circ}\text{C}$), or chronic, persistent, or recurring infection(s) requiring active treatment with antibiotics, antivirals, or antifungals within 4 weeks prior to the screening visit or other frequent recurrent infections deemed unacceptable as per Investigator judgment.
- E 18. Patients with uncontrolled diabetes mellitus, defined as Hemoglobin A1c (HbA1c) $\geq 9\%$ at the screening visit.
- E 19. Patients with nonhealed/healing skin ulcers.
- E 20. Patients who received any live, attenuated vaccine within 3 months prior to the baseline visit, such as *varicella-zoster* virus, oral polio or measles-mumps-rubella vaccines.
- E 21. Patients who had a positive test at screening for hepatitis B surface antigen (HBs-Ag) or total hepatitis B core antibody positive with negative hepatitis B surface antibody (HBs-Ab), or total hepatitis B core antibody positive with positive HBs-Ab and presence of hepatitis B virus (HBV) deoxyribonucleic acid (DNA).
- E 22. Patients who are positive for hepatitis C antibodies at the screening visit.

- E 23. Patients, who have a positive test at the screening visit or who previously had a positive test, or who are suspected to be positive for human immunodeficiency virus (HIV).
- E 24. Patients with a history of recurrent herpes zoster or active herpes zoster.
- E 25. Patients with a history of prior articular or prosthetic joint infection.
- E 26. Prior or current history of malignancy, including lymphoproliferative diseases, other than adequately-treated carcinoma in-situ of the cervix, nonmetastatic squamous cell or basal cell carcinoma of the skin, within 5 years prior to the baseline visit.
- E 27. Prior or current history of other significant concomitant illness(es) that, according to Investigator's judgment, would adversely affect the patient's participation in the study. These include, but are not limited to, cardiovascular (including stage III or IV cardiac failure according to the New York Heart Association classification), renal, neurological (including demyelinating disease), active infectious diseases, endocrinological, gastrointestinal, hepato-biliary, metabolic, pulmonary, non-malignant lymphoproliferative disease or other lymphatic disease(s).
- E 28. Any patient who has had surgery within 4 weeks prior to the screening visit or with planned surgery during the course of the study.

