- E 29. Patients with a history of a systemic hypersensitivity reaction, other than localized injection site reaction, to any biologic drug and known hypersensitivity to any constituent of the sarilumab product.
- E 30. Patients with any of the following laboratory abnormalities at the screening visit:
- Hemoglobin <8.5 g/dL.
 - White blood cells <3000/mm³.
 - Neutrophils <2000/mm³.
 - Platelet count <150 000 cells/mm³.
 - Aspartate aminotransferase (AST) or alanine aminotransferase (ALT) >1.5 x upper limits of normal (ULN), unless this is a manifestation of active GCA in the opinion of the Investigator.
 - Bilirubin (total) >ULN, unless documented Gilbert's disease diagnosed by genetic testing.
 - Presence of severe uncontrolled hypercholesterolemia (>350 mg/dL, 9.1 mmol/L) or hypertriglyceridemia (>500 mg/dL, 5.6 mmol/L).
 - Patients with a calculated creatinine clearance <30 mL/minute (using Cockcroft-Gault formula).

Note: Laboratory parameters may be repeated during the screening period if judged to be spurious or due to technical error in order to determine eligibility.

E 31. Patients with a history of inflammatory bowel disease or severe diverticulitis or previous gastrointestinal perforation.

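### E 03 applies its JAK inhibitor and biologic washouts only to use for GCA, so a patient on one of these drugs for another disease can enter without washout unless the investigator uses discretion

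*Protocol*

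**What the plan says.** The stem of E 03 in Protocol 7.2.1 is "Any prior use of the following therapies, for the treatment of GCA". Its windows before baseline are 4 weeks for JAK inhibitors, 8 weeks for abatacept and 1 week for anakinra. Cell-depleting agents are barred until B cells have recovered. TNF inhibitors have 2 weeks for etanercept and, for the others, "infliximab, certolizumab, golimumab, or adalimumab within 8 weeks", or five half-lives where that is longer.

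The exclusion list in the Clinical Trial Summary, part of a block labelled "Main selection criteria", gives windows for JAK inhibitors, TNF inhibitors, abatacept and anakinra under the stem "Prior treatment with any of the following". It has no indication limit and does not list cell-depleting agents.

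Protocol 7.2 makes the numbered list the operative one: patients "will be screened for the following exclusion criteria which are sorted and numbered in the following subsections".

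After randomisation, Protocol 10.4.3 includes use of any biologic DMARD other than the study drug among the events requiring permanent discontinuation, with no reference to indication. Protocol 8.8 bans concomitant biologics only when given for GCA. SAP 2.1.3.1 scores permanent withdrawal from study treatment before the time point as failure on the sustained-remission components.

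**The concern.** The reason a patient was given a TNF inhibitor or abatacept does not change how long it stays in the body or what it adds to sarilumab. The synopsis and the stopping rule reflect this; E 03 does not. Two consequences follow.

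The first is safety. A patient who took one of these drugs for another disease until just before baseline meets no E 03 washout and starts sarilumab with overlapping immunosuppression. Protocol 4.1 lists serious infections as an identified risk of sarilumab, and Protocol 10.7.1 notes the increased infection risk with biologics, including TNF antagonists.

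The second concerns the endpoint. A patient who stays on a biologic DMARD passes E 03 but must come off study drug under 10.4.3. The SAP then counts that patient as a failure, although neither GCA nor sarilumab caused the stop.

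**Working it through.** The plan states no figure on this point. The check is a comparison of the texts, followed by two small calculations for scale.

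**1. What E 03 leaves open for non-GCA use.** E 06 bars immunosuppressants within 4 weeks of baseline, with no indication limit. Whether it reaches the E 03 drugs is arguable, so both readings are shown, in weeks before baseline.

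| Drug | E 03 (GCA use only) | Synopsis (any use) | Open if E 06 does not reach it | Open if E 06 does |
|---|---|---|---|---|
| JAK inhibitors | 4 | 4 | 4 | 4 − 4 = 0 |
| Abatacept | 8 | 8 | 8 | 8 − 4 = 4 |
| Infliximab, certolizumab, golimumab, adalimumab | 8* | 2 to 8* (TNF class) | 8* | 8 − 4 = 4* |
| Etanercept | 2* | 2 to 8* (TNF class) | 2* | 0 (2 is less than 4)* |
| Anakinra | 1 | 1 | 1 | 0 (1 is less than 4) |
| Cell-depleting agents | until B-cell recovery | not listed | no washout | anything beyond 4 |

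*Longer where five half-lives is longer; the documents give no half-lives.

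**2. Is E 06 meant to cover these drugs?** Probably not. All its named examples are non-biologic. If it did cover them, its 4-week bar would make the 1-week anakinra window redundant, and the 2-week etanercept window too unless five half-lives exceeds 4 weeks.

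**3. Do other criteria close the gap?**
- E 04 concerns IL-6 antagonists only.
- E 07 excludes systemic corticosteroids for non-GCA conditions, so the drafters addressed non-GCA treatment there. No counterpart exists for biologics.
- E 12 (likely non-compliance) and E 27 (significant concomitant illness) could be used, but both rest on investigator judgment.
- E 31, "Patients with a history of inflammatory bowel disease or severe diverticulitis or previous gastrointestinal perforation", removes one group of likely biologic users. Rheumatoid arthritis, for example, is not named in any exclusion.

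**4. What happens to a patient who continues a biologic DMARD.** Protocol 10.4.3 requires study drug to stop, and Protocol 10.4 then also ends the prednisone taper. Under SAP 2.1.3.1, a stop before Week 12 fails the remission component. A stop before Week 24 or Week 52 fails the flare, CRP and taper components of that endpoint. A stop soon after entry therefore fails all four components of both endpoints.

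**5. Scale.** SAP Table 1 has 42 patients in the combined sarilumab groups and 41 in the combined placebo groups. One would-be responder turned into a non-responder moves a group's Week 24 rate by 1/42 = 2.4 or 1/41 = 2.4 percentage points. That is simply 1/n and would hold for any single non-responder.

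Eligibility is fixed before blinded randomisation, so affected patients should fall in all arms in proportion. If k of the 83 are affected and would otherwise have responded like the rest, the expected difference shrinks by the factor (1 − k/83). With the Table 1 rates the planned difference is 53 − 17 = 36 points. The documents do not give k; assuming 0 to 4:
- k = 0: 36.0 points
- k = 1: 36 × 82/83 = 35.6 points
- k = 4: 36 × 79/83 = 34.3 points

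**The case against.** The strongest reply is that E 06 already catches the continuing user. Its list is open and has no indication limit, and a patient still on a biologic at baseline is by definition inside 4 weeks. Protocol 8.8 specifies non-biological immunosuppressive drugs when it means them; E 06 does not. On that reading the forced stop does not arise, and only weeks 4 to 8 of prior abatacept and the four 8-week TNF inhibitors, plus incomplete B-cell recovery after cell-depleting agents, stay open. This reading is possible, but it makes shorter windows in E 03 redundant, so it is an unlikely intention and not a safeguard to rely on.

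The GCA qualifier may also be deliberate, since similar limits appear in E 08 and in 8.8. The synopsis is a shortened list and does not govern screening. Both points stand as far as they go. But shortening does not explain why the synopsis excludes more patients than the full criterion, and a deliberate choice to admit such patients does not fit a stopping rule that removes those who continue a biologic DMARD.

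It is also fair to say that an investigator aware of 10.4.3 would hardly randomise a patient who intends to stay on a biologic, and could use E 12 or E 27 to decline. That makes the event less likely without making exclusion mandatory.

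Finally, the study is closed and SAP 2.4.4.3 makes all p-values nominal. This limits what a correction can achieve now.

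**Conclusion.** The concern holds as a minor defect in the eligibility rule. As written, E 03 admits patients recently treated with these drugs for another disease without washout, and can admit some whom 10.4.3 must then take off study drug. This rests on reading E 06 as not covering the E 03 drugs and on no discretionary exclusion under E 12 or E 27. The expected effect is a safety gap plus dilution that favours no arm, of unknown and possibly zero frequency.

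A reader might infer four stronger things that the documents do not support:
- **Every patient with non-GCA use must stop study drug.** Only use of a biologic DMARD on study triggers that rule. Someone who stopped before baseline does not, and JAK inhibitors are not biologics.
- **The treatment comparison is biased in one direction.** The entry gap precedes randomisation, so it is neutral between arms in expectation, although chance imbalance is possible in small arms.
- **Such patients were enrolled.** Nothing in either document shows this.
- **Sections 8.8 and 10.4.3 contradict each other.** One is narrower, but both can be obeyed.

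**What to change.** In Protocol 7.2.1, delete the closing clause of the E 03 stem (the five words after the comma) so that every window applies whatever the indication. This brings E 03 into line with the synopsis and 10.4.3. The cost is a slightly narrower eligible population.

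Leave the GCA limit in 8.8 in place. That ban covers any biologic, a wider class than biologic DMARDs, and removing the limit would bar biologics given for unrelated purposes.

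SAP section 1 records that recruitment was suspended in March 2020 and not reopened, with 83 of 360 planned patients randomised. The edit therefore corrects the rule for the record and for reuse of the protocol text; it does not change who was randomised. Patients who met E 03 as numbered should not be reclassified as deviations.

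Optionally, and separately from the fix, the SAP could add one listing of patients with non-GCA use of an E 03 drug within its window or on study, giving drug, indication, stop date, arm and whether study drug was stopped. The tables in SAP 2.2 and 2.4.2 give discontinuation reasons and generic drug names but do not link them to indication or window. The listing assumes the medication history was collected for at least 8 weeks before randomisation; SAP 2.1.2 does not state the period.

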7.2.2 Exclusion criteria related to the current knowledge of Sanofi compound

- E 13. Pregnant or breastfeeding woman.
- E 14. Woman of childbearing potential (WOCBP) not protected by highly-effective contraceptive method(s) of birth control (as defined in [Appendix A](#)), and/or who are unwilling or unable to be tested for pregnancy.
- E 15. Exclusion related to tuberculosis (TB):
 - Active TB or a history of incompletely treated TB.
 - Quantiferon positive patients (no active disease) are excluded from the study unless the following conditions are met:
 - Patients with a history of prior documented completed chemoprophylaxis for latent tuberculosis infection (TBI) (eg, acceptable treatments would be 9 months of isoniazid 300 mg PO daily or equivalent proven regimen per local guidelines) or

treatment of active TBI, has obtained consultation with a specialist to rule out or treat active TBI.

- Patients with no prior history of chemoprophylaxis for latent TBI or treatment for active TBI, have obtained consultation with a specialist to initiate an appropriate regimen of chemoprophylaxis, based on local epidemiology and applicable guidelines and the patient has demonstrated compliance and has tolerated treatment for ≥ 1 month.
 - Consultation with and prior approval from sponsor are required in either of the aforementioned scenarios.
- Clinically significant abnormality consistent with prior/active TB infection based upon chest radiograph with at least posterior-anterior (PA) view (radiograph must be taken within 12 weeks prior to screening visit or during the screening period). Additional lateral view is recommended but not required.
 - Suspected extrapulmonary TB infection.
 - Patients at high risk of contracting TB, such as close contact with individuals with active or latent TB.
 - Patient who received Bacille Calmette Guerin (BCG)-vaccination within 12 months prior to screening.
- E 16. Patients with a history of invasive opportunistic infections, including but not limited to histoplasmosis, listeriosis, coccidioidomycosis, candidiasis, Pneumocystis jirovecii, aspergillosis despite resolution or John Cunningham (JC) virus (progressive multifocal leukoencephalopathy [PML]).
- E 17. Patients with fever associated with infection ($>38^{\circ}\text{C}$), or chronic, persistent, or recurring infection(s) requiring active treatment with antibiotics, antivirals, or antifungals within 4 weeks prior to the screening visit or other frequent recurrent infections deemed unacceptable as per Investigator judgment.
- E 18. Patients with uncontrolled diabetes mellitus, defined as Hemoglobin A1c (HbA1c) $\geq 9\%$ at the screening visit.
- E 19. Patients with nonhealed/healing skin ulcers.
- E 20. Patients who received any live, attenuated vaccine within 3 months prior to the baseline visit, such as *varicella-zoster* virus, oral polio or measles-mumps-rubella vaccines.
- E 21. Patients who had a positive test at screening for hepatitis B surface antigen (HBs-Ag) or total hepatitis B core antibody positive with negative hepatitis B surface antibody (HBs-Ab), or total hepatitis B core antibody positive with positive HBs-Ab and presence of hepatitis B virus (HBV) deoxyribonucleic acid (DNA).
- E 22. Patients who are positive for hepatitis C antibodies at the screening visit.

- E 23. Patients, who have a positive test at the screening visit or who previously had a positive test, or who are suspected to be positive for human immunodeficiency virus (HIV).
- E 24. Patients with a history of recurrent herpes zoster or active herpes zoster.
- E 25. Patients with a history of prior articular or prosthetic joint infection.
- E 26. Prior or current history of malignancy, including lymphoproliferative diseases, other than adequately-treated carcinoma in-situ of the cervix, nonmetastatic squamous cell or basal cell carcinoma of the skin, within 5 years prior to the baseline visit.
- E 27. Prior or current history of other significant concomitant illness(es) that, according to Investigator's judgment, would adversely affect the patient's participation in the study. These include, but are not limited to, cardiovascular (including stage III or IV cardiac failure according to the New York Heart Association classification), renal, neurological (including demyelinating disease), active infectious diseases, endocrinological, gastrointestinal, hepato-biliary, metabolic, pulmonary, non-malignant lymphoproliferative disease or other lymphatic disease(s).
- E 28. Any patient who has had surgery within 4 weeks prior to the screening visit or with planned surgery during the course of the study.
- E 29. Patients with a history of a systemic hypersensitivity reaction, other than localized injection site reaction, to any biologic drug and known hypersensitivity to any constituent of the sarilumab product.
- E 30. Patients with any of the following laboratory abnormalities at the screening visit:
- Hemoglobin <8.5 g/dL.
 - White blood cells <3000/mm³.
 - Neutrophils <2000/mm³.
 - Platelet count <150 000 cells/mm³.
 - Aspartate aminotransferase (AST) or alanine aminotransferase (ALT) >1.5 x upper limits of normal (ULN), unless this is a manifestation of active GCA in the opinion of the Investigator.
 - Bilirubin (total) >ULN, unless documented Gilbert's disease diagnosed by genetic testing.
 - Presence of severe uncontrolled hypercholesterolemia (>350 mg/dL, 9.1 mmol/L) or hypertriglyceridemia (>500 mg/dL, 5.6 mmol/L).
 - Patients with a calculated creatinine clearance <30 mL/minute (using Cockcroft-Gault formula).

Note: Laboratory parameters may be repeated during the screening period if judged to be spurious or due to technical error in order to determine eligibility.

E 31. Patients with a history of inflammatory bowel disease or severe diverticulitis or previous gastrointestinal perforation.

